4.2 Outcome

We hypothesise that patients will have a statistically significant improvement in self-reported quality life after CLTI clinic assessment management in comparison to before CLTI clinic assessment and management.

We propose that the POPS service will be favourably reviewed by patients when provided with a structured questionnaire.

5. Study Design and Methods of Data Collection and Data Analysis

This will be a prospective observational repeated measures study.

Patients who are referred into the CLTI clinic will be identified from the clinic register, which also distinguishes between new patients and patients who are being followed-up.

New patients who are attending the CLTI clinic will be approached to enrol into the study. Patients who consent to enrolment in the study will have their details recorded on a register which will enable the researchers to identify when the next appointments are due and can therefore determine when the next questionnaire can be delivered.

If patients consent to participate, they will be asked to complete:

- Their first EuroQol-5D questionnaire immediately prior to their first CLTI clinic appointment
- 1 feedback survey about their CLTI clinic experience after their first appointment
- A second EuroQol-5D questionnaire 6-12 weeks after their treatment is complete
- A third EuroQol-5D questionnaire at 12 months after the initial appointment

Separately, patients who are then referred from CLTI clinics to the POPS service at (based on the POPS referral criteria) will be asked if they wish to answer a structured questionnaire about the POPS service. If they agree, they will be asked to complete:

- 1 additional feedback survey about their POPS clinic experience immediately after their appointment

This is in addition to the 4 questionnaires and surveys they have completed / will be asked to complete as part of the CLTI clinic evaluation.

The anticipated study start date is 1st December 2022, with primary completion expected around 1st July 2023. The expected study completion date is 1st July 2024.

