5.1 Data collection

Data will be collected using the standardised EuroQol-5D questionnaire. This is a validated patient reported outcome measure which has been widely used in studies evaluating self-reported quality of life.

A license to use the questionnaire has been authorised and granted. The EuroQol survey will be delivered electronically using LimeSurvey software. It can be completed by study participants, with or without prompting from their carers or relatives, or researchers on behalf of study participants.

Additionally a structured questionnaire evaluating the CLTI clinic and/or POPS service using a Likert scale and free text comments will be administered to participants. We plan to use an iPad or tablet to administer the surveys to patients.

Survey responses that are entered are stored electronically within LimeSurvey, both on an app and also on a website cache. The survey itself contains no identifiable information at all.

Identifiable data will only be kept on a study registry within a password protected cloud drive attached to an NHS.net account. NHS.net is Caldicott compliant and therefore adequate for handling patient identifiable data. The purpose of this registry is to ensure that subsequent survey responses from the same patients are linked together (as it is a repeated measures design) and also to highlight when new appointments are due. This information is not contained within the EuroQol survey.

6. Study Setting

The study will take place in the outpatient suite waiting room. Patients who are attending their first CLTI appointment and have consented to participate will be given the questionnaires on a tablet computer to complete. Identifying patients from the clinic register targets the exact demographic cohort. It is a single centre study. The POPS service is also in an outpatient suite.

7. Sample and Recruitment

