7.1.2 Exclusion Criteria

Patients who have significant cognitive impairment and are unable to communicate will be excluded, as they will be unable to respond to the questions. Patients with mild cognitive impairment but still demonstrate capacity that may require prompting from carers or relatives in order to answer questions can still be included as the EuroQol-5D is validated for this purpose.

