7.3 Sample identification

The researchers will identify the participants from a list of patients due to attend CLTI clinic, by attending the clinic and receiving a copy of the appointment schedule. The research team consist of those who provide clinical care to those patients in clinic, and therefore have access to identifiable data as part of their routine clinical role. Patients who have been referred to the POPS clinic from the CLTI clinic and consented to participate will be known to the researchers directly

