7.4 Consent

Consent will be obtained in clinic, prior to the patient's first appointment. One of the research team will approach the patient, explain the nature of the study and provide them with a patient information leaflet.

There will be the opportunity to ask questions prior to consenting. Patients who have mild cognitive impairment can still be included if they demonstrate capacity and consent to enrolment, even if they require some guidance in answering. The EuroQol-5D survey can be administered to someone else on behalf of the intended study participant who can prompt the participant to respond.

8. Ethical and Regulatory Considerations

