8.1 Assessment and management of risk

There won't be any additional risks or harm to patients as a result of participation in the study because they are only required to fill out questionnaires. If patients become distressed during the provision of routine care, they can raise their issues with the

researchers who are also care providers, or any of the care providers in the CLTI clinic. Our CLTI Vascular Nurse Specialist oversees patients seen in the clinic and acts as a point of contact for patients who have questions or issues during their treatment, whether that is attending appointments, or lack of communication or pain. Patients are given a card with her direct number ([name]) and can get in contact during office hours (Mon-Fri 0800-1700). If concerns can't be addressed at this level, patients will be signposted to the Patient Experience team (PALS) on [name] or [contact]. Any safeguarding issues that are incidentally identified during the study will be communicated to the patient's GP or the adult safeguarding team.

An REC opinion will be sought and a draft IRAS form has been written in the anticipation of submitting it. The study will not begin until the relevant REC has reviewed and approved the proposal.

Amendments to the study will require a valid notice of amendment to the REC for consideration. This will be discussed with the Chief Investigator first.

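### Section 5.1 lets researchers complete the EQ-5D for participants without requiring that the answers be the participant's own, although the researchers also treat these patients

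*Protocol*

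**What the plan says.** Section 4.2 sets the hypothesis: "We hypothesise that patients will have a statistically significant improvement in self-reported quality life after CLTI clinic assessment management". Section 5 describes an observational repeated-measures design with three EQ-5D forms per patient. The first is described as "Their first EuroQol-5D questionnaire immediately prior to their first CLTI clinic appointment". The second falls 6-12 weeks after treatment is complete, and the third 12 months after the initial appointment. No comparison group is described.

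On completion, section 5.1 says: "It can be completed by study participants, with or without prompting from their carers or relatives, or researchers on behalf of study participants". Section 7.4 adds: "The EuroQol-5D survey can be administered to someone else on behalf of the intended study participant who can prompt the participant to respond".

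On who the researchers are, section 7.3 says: "The research team consist of those who provide clinical care to those patients in clinic". Section 8.1 again refers to "researchers who are also care providers, or any of the care providers in the CLTI clinic".

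Other sections bear on whose answers are meant. Section 6 says: "Patients who are attending their first CLTI appointment and have consented to participate will be given the questionnaires on a tablet computer to complete". Section 7.1.2 excludes patients with severe cognitive impairment who cannot communicate, "as they will be unable to respond to the questions". It admits those with mild impairment who have capacity, with carers or relatives prompting.

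**The concern.** A self-reported outcome depends on the patient choosing the response. Section 5.1 gives researchers a role in completing the form and puts no limit on it. Someone working from 5.1 alone could choose the responses for a patient and still comply with the protocol. Because the research team runs the clinic, that person would be supplying the outcome by which the clinic is assessed.

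The design leaves little protection against this. The first form precedes any contact with the clinic, and the later two follow assessment and treatment by the same team. There is no control group in which a similar effect of staff involvement would appear and cancel. The need for help is foreseeable: section 1 says that up to 50% of CLTI patients have significant frailty, and 7.1.2 admits patients with mild cognitive impairment. The protocol describes no record of how each form was completed, so an effect of completion mode could not be examined later.

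**Working it through.** The protocol gives no figure to reproduce. The check compares the passages and then asks what can be said about size.

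**Step 1: possible readings of 5.1.**

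- *Proxy.* The researcher decides the responses. This fits the words of 5.1 but conflicts with the self-reported outcome in 4.2, with section 5 (patients are asked to complete each form), with section 6 (the patient is given the tablet) and with the reason for exclusion in 7.1.2.
- *Data entry.* The researcher keys in what the patient says. This fits 5.1 and is consistent with the other sections.
- *Prompting.* The clause can be parsed as adding researchers to the carers and relatives who may prompt. This is also consistent with the outcome, although 7.1.2 names only carers and relatives as prompters.

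Two of the three readings are harmless to the definition of the outcome. Section 5.1 does not choose among them, and on none of them does it state whose answers are recorded.

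**Step 2: does 7.4 settle it?** The sentence opens as if the survey were given to another person in the patient's place, and ends with that person prompting the patient. It can be read as a proxy answering or as a helper assisting. It does not name researchers, so it neither limits the permission in 5.1 nor adds to the concern about the treating team.

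**Step 3: route into the result.** For time point *t*, let *p_t* be the share of forms with staff involvement and *d_t* the mean shift in score on such a form. Then

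expected observed mean change = true mean change + (*p_2 d_2* − *p_1 d_1*),

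with 1 the first form and 2 either later form. The extra term is zero if staff involvement does not affect answers, or if its overall effect is equal at both times. Otherwise it stays in the paired change, and no comparator removes it.

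**Step 4: size.** The protocol gives no value for *p_1*, *p_2*, *d_1* or *d_2*, and nothing that fixes their signs. Neither the size nor the direction of the extra term can be derived, so none is given.

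**The case against.** The strongest reply is that the protocol, read as a whole, already means assisted self-report. Patients who cannot respond are excluded, those with mild impairment must have capacity, the patient is handed the tablet, and 7.4 ends with the participant responding. No enrolled group appears to need a proxy. On a tablet survey, completing a form for someone may mean no more than entering the answers they give. This stands as evidence of intent and limits the weight of the point. It does not supply the missing rule, because staff have to infer the limit from other sections.

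A reader might infer that the clinic team plans to score its own patients, or that the result will be biased in the clinic's favour. The documents support neither. No passage plans proxy scoring, the proxy reading of 5.1 is only one of three, and the direction of any shift is unknown.

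It is also fair to say that an analysis by completion mode may be left to a statistical analysis plan. Its absence from the protocol is not part of this point. Such an analysis does, however, need the mode to be recorded when the form is filled in.

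**Conclusion.** The point holds as a minor correction. Section 5.1 states a permission that is too wide for a self-reported outcome. On one literal reading it conflicts with sections 4.2, 5, 6 and 7.1.2, and the matching sentence in 7.4 is unclear. That the researchers are the treating team is stated twice and is not in doubt.

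The consequence is conditional. It arises only if staff supply answers, or if the effect of their help differs between the first and later forms. The conclusion rests on the wording and on the uncontrolled before-after design, not on any assumed rate of assistance.

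**What to change.** In 5.1, replace the clause on who may complete the form with: *All answers must be the participant's own; carers or relatives may prompt, and researchers may only read items aloud and enter the participant's answers.* Reword the 7.4 sentence to say the same. Section 7.1.2 needs no change, since it already has the patient answering with prompting from carers or relatives.

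Add one non-identifying LimeSurvey field at each of the three time points: self-completed, prompted by carer or relative, or entered by researcher. The rule removes the proxy reading. It does not remove any effect of having a treating clinician read out the items, and the field allows that to be examined.

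The cost is wording in two sections, one survey field and minor data entry. If approval has already been given, section 8.1 requires a notice of amendment to the REC. The change excludes no patient: those who can answer but cannot manage a tablet alone can still be helped and remain in the main analysis.

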7.1.1 Inclusion Criteria

All CLTI patients seen and enrolled in the CLTI clinic are eligible.

7.1.2 Exclusion Criteria

Patients who have significant cognitive impairment and are unable to communicate will be excluded, as they will be unable to respond to the questions. Patients with mild cognitive impairment but still demonstrate capacity that may require prompting from carers or relatives in order to answer questions can still be included as the EuroQol-5D is validated for this purpose.

7.2 Sampling

We will adopt a convenience sampling strategy. The rationale for this strategy is the available pool of respondents who attend the CLTI clinic. We have chosen a sample size of between 50 – 100 patients. The CLTI clinic runs 3 times weekly and attempts to see 3-4 new patients per clinic, which means on average 9 – 12 patients per week. This would mean we should achieve our sample in around 10 weeks. However, pragmatically speaking, not every clinic will have the same number of new patients, not every patient will be suitable and some patients will be lost to follow-up. Hence we have a range of between 50 – 100 responses would be sufficient.

There is no set amount of structured feedback questionnaire responses required, either of the CLTI or POPS clinic.

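### Does Section 7.2 leave no room for loss to follow-up by giving 50–100 both as the patients sampled and as the responses needed?

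*Protocol*

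**What the plan says.** Section 7.2 of the protocol states the sample size in patients: "We have chosen a sample size of between 50 – 100 patients". It gives the supply as three clinics a week with 3–4 new patients each, that is 9–12 a week, and infers: "This would mean we should achieve our sample in around 10 weeks". It then tempers this. Clinics will vary in their number of new patients, and "not every patient will be suitable and some patients will be lost to follow-up". The conclusion drawn is "Hence we have a range of between 50 – 100 responses would be sufficient". The next paragraph takes the feedback surveys out of the count: "There is no set amount of structured feedback questionnaire responses required, either of the CLTI or POPS clinic".

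Three other statements bear on what a response is:

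- The hypothesis in Section 4.2 sets quality of life after clinic management "in comparison to before CLTI clinic assessment and management".
- Section 5 plans three EuroQol-5D questionnaires per patient: one just before the first appointment, then "A second EuroQol-5D questionnaire 6-12 weeks after their treatment is complete", and one at 12 months after the initial appointment.
- Section 5.1 keeps a registry so that "subsequent survey responses from the same patients are linked together (as it is a repeated measures design").

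The protocol gives no loss rate, effect size, standard deviation, power or target precision.

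**The concern.** A sample size is normally stated either as the number to enrol or as the number expected to be analysable, with an allowance for loss linking the two. Section 7.2 appears to use one range for both. It names patients, expects loss, and ends with the same numbers in a different unit.

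Because the feedback surveys have no required number, the responses can only be EuroQol-5D responses. Because the hypothesis is a before-after comparison on linked data, the natural unit is a patient with a baseline and a follow-up score, although the text does not say so. On that reading a team could stop at 50 patients, comply with the opening sentence, lose one, and fall short of the closing sentence. The last questionnaire comes at 12 months, so the shortfall might appear only after enrolment had closed. At stake would be the number of pairs behind the main comparison and the clarity of when recruitment may stop.

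**Working it through.** **Inputs.** From Section 7.2: 50–100 patients; 50–100 responses; 3 clinics a week; 3–4 new patients per clinic; about 10 weeks. From Section 5: three EuroQol-5D forms per patient. The loss rates of 20–40% used below are assumptions, since the protocol gives none.

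**Reproducing the plan's own figure.** The range 50–100 cannot be derived, because no inputs to a power or precision calculation are given. The accrual statement can be checked.

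- Weekly supply: 3 × 3 = 9 to 3 × 4 = 12.
- Ten weeks: 9 × 10 = 90 to 12 × 10 = 120.
- Time for 100 patients: 100/12 = 8.3 to 100/9 = 11.1 weeks.
- Time for 50 patients: 50/12 = 4.2 to 50/9 = 5.6 weeks.

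The 10-week figure therefore matches a sample of about 100, not 50.

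**How much loss leaves 50 pairs.** With N enrolled, the largest loss that still leaves 50 expected pairs is 1 − 50/N.

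| Enrolled | Loss tolerated |
|---|---|
| 50 | 0% |
| 52 | 3.8% |
| 55 | 9.1% |
| 60 | 16.7% |
| 80 | 37.5% |
| 100 | 50% |

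The zero allowance exists at exactly 50 and nowhere else in the range.

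**Which losses count.** Section 7.2 gives three reasons for the range: variable clinic numbers, unsuitable patients and loss to follow-up. The first two limit how many are enrolled. Only the third reduces the number of pairs among those enrolled. Even then, two follow-up forms are planned, so a patient lost between the second and third still has a before-after pair at the earlier time point.

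**What fewer pairs would cost.** In units of the standard deviation of change, the 95% half-width is t(0.975, n − 1)/√n.

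- 50 pairs: 0.284.
- 50 enrolled, 20% loss: 50 × 0.8 = 40 pairs, 0.320.
- 50 enrolled, 40% loss: 50 × 0.6 = 30 pairs, 0.373.
- 100 enrolled, 20% loss: 100 × 0.8 = 80 pairs, 0.223.
- 100 enrolled, 40% loss: 100 × 0.6 = 60 pairs, 0.258.

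In the worst of these cases the interval is 0.373/0.284 = 1.31 times as wide as with 50 pairs.

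**The case for a change.** The strongest case for a change is that the range is the only size figure in the protocol and it does not say what it counts. If single forms were meant, 50 patients could supply up to 50 × 3 = 150; if linked pairs were meant, they supply at most 50. The same sentence therefore implies different stopping points. Section 7.2 does name 50 patients as an acceptable sample, and at the stated rate that number could be reached in 4.2 to 5.6 weeks. Nor can this be put down to detail left for an analysis plan, because the protocol has already fixed both numbers. One added sentence would settle it at almost no cost.

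The description of the text stands: the unit shifts and is undefined. The consequence does not follow. The order of the argument in Section 7.2 is that full clinics would give about 100 in 10 weeks, that practice will fall short of this for three listed reasons, and that a range is therefore given. Read that way, the range is the allowance, and both sentences describe the same final sample loosely. Stopping is also not left wholly open. Study completion on 1 July 2024 with a 12-month questionnaire implies last first appointments around 1 July 2023, well beyond the time needed for 50 at the stated rate. Finally, 50 is not tied to any power or precision, so 49 or 40 pairs would fail no criterion that the study relies on.

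**Conclusion.** No change to the plan follows. Section 7.2 is loosely worded, but the supposed contradiction needs three things together: enrolment of exactly 50, a requirement of 50 linked pairs that the protocol does not state, and a loss at the particular time point that counts. On the more natural reading, about 100 sought and as few as 50 accepted, there is no expected shortfall up to 50% loss.

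If enrolment did end at 50, the cost would be precision: a half-width of 0.32–0.37 standard deviations of change in place of 0.28, under an assumed 20–40% loss. Followed as written, the plan still gives a before-after estimate from the linked pairs obtained, with an interval that reflects their number. Restating the range as two figures would alter neither that estimate nor its interval. An analyst will naturally report the number enrolled and the number with paired scores at each time point, and that report resolves the ambiguity.

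This conclusion does not say that 50–100 is large enough, since the protocol gives no inputs with which to test that. It rests on the reading of the accrual sentence and on the assumed loss rates.

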7.3 Sample identification

The researchers will identify the participants from a list of patients due to attend CLTI clinic, by attending the clinic and receiving a copy of the appointment schedule. The research team consist of those who provide clinical care to those patients in clinic, and therefore have access to identifiable data as part of their routine clinical role. Patients who have been referred to the POPS clinic from the CLTI clinic and consented to participate will be known to the researchers directly

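### CLTI clinic feedback, and possibly POPS feedback, is at risk of favourable-response bias because no described step separates the rating from the treating team

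*Protocol*

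**What the plan says.** **Who runs the study.** Protocol section 7.3 says of the people who identify participants: "The research team consist of those who provide clinical care to those patients in clinic". Section 8.1 confirms the dual role by referring to "researchers who are also care providers". Consent is taken in clinic before the first appointment: "One of the research team will approach the patient, explain the nature of the study" (section 7.4).

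**When and how feedback is taken.** Section 5 asks for "1 feedback survey about their CLTI clinic experience after their first appointment", without giving an interval. For patients referred on to POPS it asks for "1 additional feedback survey about their POPS clinic experience immediately after their appointment". Section 5.1 adds that "a structured questionnaire evaluating the CLTI clinic and/or POPS service using a Likert scale and free text comments will be administered to participants", by tablet. Section 6 places the study in the outpatient waiting room and says that POPS also runs in an outpatient suite.

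**What is expected.** Section 4.2 states: "We propose that the POPS service will be favourably reviewed by patients when provided with a structured questionnaire". For the CLTI clinic, section 4.2 predicts only an improvement in quality of life. The expectation that patients will review CLTI clinics well appears in the rationale (section 2), as background.

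**Safeguards.** The survey holds no identifiers (section 5.1). The registry that links a patient's responses is open only to the Principal and Chief Investigators (section 8.4).

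**The concern.** A patient with a limb-threatening condition is asked to rate a service at about the time of the visit, in a study run by clinicians who provide that service and on whom further treatment depends. Courtesy and dependence push such ratings upwards. There is no comparator, so nothing in the design would show how much of a good rating came from the circumstances in which it was given.

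This is a matter of data collection. Who is nearby, who enters the answers and what the patient is told are settled when the survey is taken, and no later analysis can undo them. A larger number of responses narrows the interval around the shifted value and does not move it back.

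At stake is how far a favourable feedback result can be believed. The quality-of-life question rests on the EuroQol, which asks about the patient's own health and not about the service, so this point does not touch it.

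**Working it through.** The protocol gives no target share, threshold or required number for the feedback surveys (section 7.2 says none is set), so there is no figure to reproduce. The check is first a comparison of the text for each survey, then an illustration under stated assumptions.

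**Step 1: what is documented for each survey**

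| Element | CLTI feedback | POPS feedback |
|---|---|---|
| Researchers also treat the raters in the rated service | Yes (7.3, 8.1) | Not stated. POPS is a separate service (1); the researchers know its patients directly (7.3) |
| Timing | After first appointment, interval not given (5) | Immediately after the visit (5) |
| Mode and place | Tablet, outpatient waiting room (5.1, 6) | Tablet, outpatient suite (5.1, 6) |
| Who hands over the tablet or is present | Not stated | Not stated |
| Researcher may enter answers | Stated for the EuroQol only (5.1) | Stated for the EuroQol only (5.1) |
| Favourable review predicted in 4.2 | No (rationale only, section 2) | Yes |

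The documented overlap of roles therefore belongs to the CLTI survey, and the documented prediction belongs to the POPS survey. What they share is that no separation of the rating from the care team is described.

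**Step 2: illustration of size**

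Let t be the true favourable share and s the share of patients with an unfavourable view who nevertheless answer favourably. Then

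observed share = t + (1 − t) × s.

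The value of s is an assumption; the protocol offers nothing to fix it.

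- t = 0.50: s = 0.10 gives 0.50 + 0.50 × 0.10 = 0.55; s = 0.30 gives 0.65.
- t = 0.60: s = 0.10 gives 0.60 + 0.40 × 0.10 = 0.64; s = 0.30 gives 0.72. At a more pessimistic s = 0.50 it is 0.80.
- t = 0.70: s = 0.10 gives 0.70 + 0.30 × 0.10 = 0.73; s = 0.30 gives 0.79.

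**Step 3: against sampling error**

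Taking n as the study's own 50 to 100 patients (also an assumption here, and POPS responses may be fewer), the standard error at 60% is √(0.6 × 0.4 / 50) = 0.069 and √(0.6 × 0.4 / 100) = 0.049. For s = 0.10 to 0.30 the shift is 4 to 12 points:

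- n = 50: 0.04 / 0.069 ≈ 0.6 to 0.12 / 0.069 ≈ 1.7 standard errors.
- n = 100: 0.04 / 0.049 ≈ 0.8 to 0.12 / 0.049 ≈ 2.4 standard errors.

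**Step 4: effect on a conclusion**

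The protocol names no test for the feedback. Suppose a favourable review were claimed when an exact one-sided 2.5% test rejects a share of 50%, and the truth is exactly 50%.

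| n | Favourable answers needed | s = 0 | s = 0.10 | s = 0.20 | s = 0.30 |
|---|---|---|---|---|---|
| 50 | 33 | 1.6% | 7.7% | 23.7% | 50.6% |
| 100 | 61 | 1.8% | 13.4% | 46.2% | 82.8% |

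With any non-zero s shown, the chance of a wrong favourable claim is higher at 100 responses than at 50.

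**The case against.** The strongest reply is that several tempting readings go beyond the text. Much of it stands.

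- *Both surveys are biased towards what section 4.2 predicts.* A reader might infer this, but 4.2 predicts a favourable review for POPS only. Nor can bias be shown from the protocol; only a risk with a plausible direction can.
- *The treating team administers both surveys.* The overlap is documented for the CLTI clinic. Section 1 describes POPS as separate, and nowhere are its staff said to be researchers or to hand out its survey. The remark in section 7.3 that the researchers know these patients explains how participants are found, not who collects ratings.
- *Patients answer in front of their clinicians, who may enter the answers.* Who is present is not stated, and completion by researchers is mentioned for the EuroQol only.
- *Patients are never told who sees their answers.* Section 7.4 provides an information leaflet, which is not among the documents reviewed, so its silence cannot be assumed.

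It is also fair that feedback is the additional, exploratory aim (section 4.1), that no number of responses is required, and that POPS serves older and frail patients, some of whom would not respond without help.

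The safeguards in sections 5.1 and 8.4 count, but only in part. They protect answers in storage and do not relieve pressure felt while answering. Responses from the same patient can still be linked, and the two people with access lead a team of treating clinicians. With 3 to 4 new patients per clinic (section 7.2), a free-text comment might also be attributable without a name.

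**Conclusion.** The point holds in a limited form. CLTI clinic feedback is at risk of favourable-response bias because it is taken on site, around the appointment, in a study run by the patients' own CLTI clinicians, with no described separation. POPS feedback may share the risk, and since it carries the only stated prediction of a favourable review, that prediction would be weakly tested if it does. The POPS link remains an inference.

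The size is unknown. The 4 to 12 point shift at a true share of 60% rests wholly on the assumed 10% to 30% switching rate, and the error rates above rest in addition on an assumed test and on n = 50 to 100. They show that a modest shift could matter at this sample size; they are not estimates. Because the feedback is secondary and the quality-of-life question is untouched, this is an inexpensive improvement and not a flaw in the main comparison.

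**What to change.** In sections 5.1 and 6, state for both feedback surveys:

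1. The participant completes the survey in private, or with their own carer. Treating clinicians, and researchers who treat that patient, step away and do not enter answers.
2. Where help is needed and no carer is present, existing clinic staff not involved in that patient's care may assist, or a LimeSurvey link is offered.
3. The opening screen says that answers carry no name, are reported only in pooled form and do not affect care.
4. The numbers of surveys offered and completed are reported for each clinic.

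A promise that the clinical team will see pooled results only should not be made. The research team is itself the clinical team, and section 8.4 lets its members do the analysis. Nor is it necessary to unlink feedback from the registry: that would be a trade-off, because linkage allows responders to be described in a convenience sample.

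The cost is a few sentences of protocol text and one survey screen. The downside is somewhat fewer completed surveys, perhaps more so among frail patients, which is why item 4 is needed.
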